5. BASELINE CHARACTERISTICS

5.1. Demographics and Baseline Characteristics

Participant demographic data (eg, sex, race, race category, ethnicity, age, and age group [< 18 , $\geq 18 - < 65$, ≥ 65 years]) and baseline characteristics (eg, body weight, height, body mass index [BMI] and BMI group [< 20 , $\geq 20 - < 30$, ≥ 30 kg/m²]) will be summarized by treatment group and overall using descriptive statistics (n, mean, SD, median, Q1, Q3, minimum, and maximum) for continuous data and by the number and percentage of participants for categorical data. The summaries of demographic data and baseline characteristics will be provided for the Safety Analysis Set.

For categorical data, the Cochran-Mantel-Haenszel (CMH) test (ie, general association statistic for nominal data and row mean scores differ statistic for ordinal data) will be used to compare the 2 treatment groups. For continuous data, the 2-sided Wilcoxon rank sum test will be used to compare the 2 treatment groups.

Similar summaries will be produced for the following subgroups: kidney disease status (as defined in Section 3.4), high-flow oxygen requirement (Yes, No), and region (US vs. ex-US).

A by-participant demographic listing will be provided.

5.2. Other Baseline Characteristics

The following baseline disease characteristics will be summarized by treatment group and overall using descriptive statistics:

- Kidney disease status (as defined in Section 3.4)
- High-flow oxygen requirement (Yes, No)
- Region (US, ex-US)
- Clinical status (8-point ordinal scale)
- Oxygen support status
- RRT at baseline
- Duration of hospitalization prior to first dose of study drug
- Duration of symptoms prior to first dose of study drug (as a continuous variable, and a categorical variable with categories of ≤ 5 and > 5)
- Duration from SARS-CoV-2 positive result to first dose of study drug

- Alanine aminotransferase (ALT)
- Baseline risk factor (as defined in Section 3.4 except BMI)
- COVID-19 vaccine (See [Appendix 2](#)) status

For categorical data, the CMH test (ie, general association statistic for nominal data and row mean scores differ statistic for ordinal data) will be used to compare the 2 treatment groups. For continuous data, the 2-sided Wilcoxon rank sum test will be used to compare the 2 treatment groups.

Similar summaries will be produced for the following subgroups: kidney disease status (as defined in Section 3.4), high-flow oxygen requirement (Yes, No), and region (US vs. ex-US).

A by-participant listing will also be provided.

5.3. Medical History

General medical history data will be collected at screening. It will be coded using the current version of MedDRA.

A summary table will present the percentages of participants reporting each medical history preferred term, sorted first in alphabetical order by system organ class (SOC) and then by preferred term (PT) in descending order of total frequency within SOC. A listing of medical history will be provided.

A by-participant listing of kidney transplant history will also be provided.

6. EFFICACY ANALYSES

6.1. Primary Efficacy Endpoint

6.1.1. Definition of the Primary Efficacy Endpoint

The primary endpoint is the composite of all-cause mortality or IMV from date of first dose through Day 29.

6.1.2. Statistical Hypothesis for the Primary Efficacy Endpoint

Null hypothesis: There is no difference between treatment groups in the probability of all-cause mortality or IMV through Day 29.

Alternative hypothesis: The probability of all-cause mortality or IMV through Day 29 is different between treatment groups.

6.1.3. Primary Analysis of the Primary Efficacy Endpoint

The primary endpoint will be analyzed using a stratified log-rank test stratified by the randomization strata. P value and the proportion of all-cause mortality or IMV at Day 29 from Kaplan-Meier estimate will be provided.

The hazard ratio and 95% confidence interval (CI) will be estimated using a Cox model with stratification factors as covariates.

Participants with missing outcomes for the primary endpoint due to premature discontinuation of the study on or prior to Day 29 will be censored at the last study day.

Additionally, the difference in proportions of all-cause mortality or IMV at Day 29 between treatment groups and the 95% CI for the difference will be provided based on the stratum-adjusted Mantel-Haenszel (MH) proportion as described in {Koch 1989} in [Appendix 2](#).

The FAS will be the primary analysis set for efficacy endpoint evaluation.

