5. INVESTIGATIONAL MEDICINAL PRODUCTS

5.1. Randomization, Blinding, and Treatment Codes Access

5.1.1. Randomization

Participants who meet screening and randomization eligibility criteria will be randomized in a 2:1 ratio to RDV or saline as placebo starting on Day 1 and assigned a participant number. Randomization will be stratified by:

- ESKD requiring chronic dialysis
- High-flow oxygen requirement
- Region (US vs ex-US)

No more than 20% of enrolled participants will have ESKD requiring chronic dialysis.

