8.5. Efficacy Analysis

8.5.1. Primary Analysis

The primary clinical end point is the composite of all-cause mortality or IMV from date of first dose through Day 29.

The primary end point will be analyzed using a stratified log-rank test stratified by the randomization stratum. The hazard ratio and 95% confidence interval will be provided. The null hypothesis being tested is that there is no difference between treatment groups in the probability of death or IMV through Day 29.

Participants with missing outcomes for the primary end point due to premature discontinuation of the study on or prior to Day 29 will be censored at the date of last contact.

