8.7. Adjustments for Multiplicity

The overall two-sided Type I error rate of 0.05 for the primary and key α -controlled secondary end points will be controlled using the Lan-DeMets approach with O’Brien-Fleming type spending function accompanying a gatekeeping testing strategy (ie, the primary efficacy end point will be tested first and the key α -controlled secondary end point will be tested only if the primary efficacy end point is met). The α -spending and gatekeeping details are specified in Table 5.

Table 5. Gatekeeping and Boundaries for Efficacy Analysis

Efficacy Analysis	Primary End Point	Key α -controlled Secondary End Point (Will be Tested ONLY IF Primary End Point is Met)
Interim Analysis (50% of Participants Completed Day 29)	0.0031	0.0031
Primary Analysis (All Participants Completed Day 29)	0.0490 (will be tested ONLY IF the primary end point is NOT met at interim)	0.0490

Note: P-values are based on two-sided stratified log-rank test.

CCI [REDACTED]

7 [REDACTED]

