2.4. Change from Protocol-Specified Analyses

The second formal DMC analysis was not performed due to the stop of study enrollment prior to reaching 50% of planned enrollment. The reason for stopping enrollment was that it became clear the study would not fully enroll in a reasonable timeframe even after implementing enrollment mitigation strategies. The decision to stop study enrollment was documented in the 16 December 2021 Study Management Team meeting minutes.

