6.2.1. Analysis of Secondary Efficacy Endpoints

The key α -controlled secondary endpoint of all-cause mortality through Day 29 will be analyzed in a similar manner to the primary endpoint.

Initiation of IMV through Day 29 and time to recovery through Day 29 will also be analyzed in a similar manner to the primary endpoint except that a competing risk analysis approach will be used with death as the competing risk.

For analysis on time to recovery through Day 29, two sets of analyses will be conducted:

(1) Time to recovery through Day 29, in which the first recovery without further worsening in the ordinal scale score (ie, a score of > 4) by Day 29 will be considered an event; (2) Time to recovery through Day 29, in which the first recovery (regardless of further worsening or not) will be considered an event.

The clinical status assessed by the 8-point ordinal scale at Day 15 and Day 29 will be analyzed using a proportional odds model including treatment as the independent variable. Two models will be explored; one with baseline score as a continuous covariate and one without baseline score as a covariate. The odds ratio and 95% CI will be provided. The percentage of participants in each category will be summarized by treatment group. The assumption of odds proportionality will be assessed using a score test and reported. Clinical status by study day and change from baseline up to Day 29 will also be summarized by treatment group.

For participants without ESKD at baseline, the number of RRT-free days will be calculated between date of first dose and Day 29. The number of RRT-free days will be calculated as the number of full days from Day 1 to Day 29 that the participant was alive and did not receive RRT. The number of RRT-free days will be summarized by treatment group, and compared between treatment groups using Wilcoxon rank sum test.

The proportion of participants with recovery through Day 29 will be summarized by treatment group, and compared between treatment groups using the CMH test stratified by randomization strata. Similar for time to recovery analysis, two sets of analyses will be conducted: (1) The proportion of participants with recovery through Day 29, in which recoveries without further worsening by Day 29 is considered; (2) The proportion of participants with recovery through Day 29, in which recoveries regardless of worsening status by Day 29 is considered.

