	Prothrombin Time (PT)	Increase	Prothrombin Time (Increased)
	Activated partial thromboplastin time (aPTT)	Increase	Activated partial thromboplastin time (Increased)

21) SAS codes for the treatment comparison for demographics and baseline characteristics tables.

CMH test for nominal variable (Y), the p-value from the general association test should be used for nominal variables:

```
proc freq;  
tables trt * Y /cmh; /*general association test*/  
run;
```

CMH test for ordinal variable (Y), the p-value from the row mean score test should be used for ordinal variables:

```
proc freq;  
tables trt * Y / cmh2 ; /*row mean score test*/  
run;
```

Wilcoxon rank sum test for continuous variable (Y), the p-value from the normal approximation two-sided test should be used for continuous variables:

```
proc npar1way wilcoxon;  
class trt;  
var Y;  
run;
```

22) Proportional Odds

A proportional odds model including treatment as the independent variable and baseline score as a continuous covariate to compare the treatment groups:

```
proc logistic;  
class trt/ param=ref order=data;  
model outcome(descending)= trt baseline;  
run;
```

A proportional odds model including treatment as the independent variable to compare the treatment groups (without covariate):

```
proc logistic;  
class trt/ param=ref order=data;  
model outcome(descending)= trt;  
run;
```

where outcome is the ordinal scale response at Day 15 and Day 29.

23) Cox model :

a) with stratification factors as covariates

```
proc phreg;  
class trt strat1 strat2 strat3;  
model aval*cnsr(1) = trt strat1 strat2 strat3 /risklimits = wald;  
ods output ParameterEstimates=Est1 ModelANOVA = pvout1;  
run;
```

b) with no stratification factors as covariates

```
proc phreg;  
class trt;  
model aval*cnsr(1) = trt /risklimits = wald;  
ods output ParameterEstimates=Est1 ModelANOVA = pvout1;  
run;
```

24) log-rank test

Log-rank test between treatment groups:

```
proc lifetest;  
time aval*cnsr(1);  
strata trt;  
run;
```

The binary indicator variable (cnsr) with a value of 0 indicates the time to the event of interest is complete or 1 indicates the time to the event is censored.

25) Stratified log-rank test

Log-rank test between treatment groups:

```
proc lifetest;  
time aval*cnsr(1);  
strata strat1 strat2 strat3/group=trt;  
run;
```

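### Clinical status has two proportional-odds models with no named lead and no entry in SAP 6.4; pairing a log-rank p-value with a main-effects Cox interval is an optional refinement only

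*SAP*

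**What the plan says.** **Clinical status (Day 15, Day 29).** Protocol 8.5.2 specifies a single proportional-odds model with treatment as the only term. SAP 6.2.1 begins with that model, then says that two will be explored: one adding baseline score as a continuous covariate, one without it. Appendix 2 item 22 gives code for both and lists the baseline-score model first. Neither contains the randomisation factors. SAP 6.4 records only the merging of the primary and final analyses. SAP 3.5 leaves this endpoint outside the multiplicity control.

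**Primary endpoint and mortality.** SAP 6.1.3 takes the p-value from a log-rank test stratified by the randomisation strata. Item 25 codes it as "strata strat1 strat2 strat3/group=trt", which crosses three binary factors into up to eight cells. For the estimate, SAP 6.1.3 says: "The hazard ratio and 95% confidence interval (CI) will be estimated using a Cox model with stratification factors as covariates". Item 23(a) codes that as "model aval*cnsr(1) = trt strat1 strat2 strat3 /risklimits = wald": main effects, one shared baseline hazard, Wald limits. SAP 6.2.1 carries this over to the key secondary endpoint: "all-cause mortality through Day 29 will be analyzed in a similar manner to the primary endpoint". Protocol 8.5.1 names no model for the estimate, saying only: "The hazard ratio and 95% confidence interval will be provided". The note to Table 5 in Protocol 8.7 fixes the test: "P-values are based on two-sided stratified log-rank test".

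**The concern.** Two models on two days give four odds ratios for clinical status, and the SAP does not rank them. The two models also estimate different quantities: an odds ratio conditional on baseline score is generally further from 1 than the unadjusted one when baseline score is prognostic. If they fall on opposite sides of 0.05, the SAP does not say which was meant to carry the conclusion, and the choice could be made after the results are seen. Because the added model is not listed as a change, a reader comparing protocol and report gets no warning. The protocol's model also leaves unused a baseline measurement that is already collected.

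The second matter is smaller. For the primary endpoint and mortality, the published interval is not built on the strata used by the test that decides success. In a borderline result the interval could exclude 1 beside a non-significant p-value, or the reverse.

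**Working it through.** **1. Which model leads?** The order of mention does not settle it: SAP 6.2.1 opens with treatment-only, and item 22 lists the baseline-score model first. Only Protocol 8.5.2 points to one model, the treatment-only one.

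**2. Clinical status, simulated.** The plan gives no power or effect figure for this endpoint, so every input except sample size is an assumption. Enrolment ended "due to the stop of study enrollment prior to reaching 50% of planned enrollment" (SAP 2.4); 0.5 × 1116 = 558, so N is at most 557. Assumed: N = 250–557, a placebo Day 29 distribution, baseline scores 4–6 with score 6 equal to high-flow oxygen, true odds ratio 1.5 or 1.0, and Wald tests. There were 27 scenarios at each odds ratio, about 3000 trials each.

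| Quantity | Result |
|---|---|
| Two SAP models disagree at 0.05, OR 1.5, high-flow OR 1.5–3 | 2.5–7.7% |
| Same, high-flow OR 5 | 8.9–12.9% |
| Baseline-score model is the significant one when they disagree, OR 1.5 | 55–90% |
| Power gained from baseline score | 0.3–10.3 points (median 3.2) |
| Further gain from the three strata | 0.3–1.6 points (2.1–2.6 if ESKD OR 2 and region OR 1.5) |
| At least one of the two models significant, OR 1.0 | 4.7–6.7% |

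Consistency check: if the models disagree in a share D of trials and the baseline-score model is the significant one in a share f of those, the net power gain is D × (2f − 1). If the extremes coincide, 12.9 × (2 × 0.90 − 1) = 10.3 points and 2.5 × (2 × 0.55 − 1) = 0.25 points, which agrees with the range shown. The Monte Carlo error of the largest disagreement rate is √(0.129 × 0.871/3000) = 0.6 points.

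A second simulation (N = 250–400, OR 1.5, also with assumed inputs) gave 6–16% disagreement, 0–12 points from baseline score and 0.3–1.9 more from the strata. Together the two give roughly 3–16% disagreement.

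**3. Why the strata add little.** Score 6 covers noninvasive ventilation or high-flow oxygen (Protocol 6.9). Noninvasive ventilation is excluded at entry (Protocol 4.3), so score 6 at baseline largely duplicates the high-flow factor.

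**4. Primary endpoint: the plan's own figure.** The RDV event rate is 1 − 0.65^0.70 = 26.0%. Expected events are 744 × 0.2603 + 372 × 0.35 = 323.9. Power is Φ(√(323.9 × 2/9) × |ln 0.70| − 1.96) = Φ(1.07) = 85.7%, against the stated 85% or so. At N = 558 (161.9 events) it is 57.1%, so borderline results are plausible.

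**5. Log-rank verdict against Cox interval, simulated.** Inputs: N = 250–557; 2:1 allocation; ESKD share 20%, the ceiling in Protocol 5.1.1 ("No more than 20% of enrolled participants will have ESKD requiring chronic dialysis"); placebo rate 35% (SAP 1.3) or 25%. Assumed: high-flow share 10–30%, US share 50% or 80%, prognostic effects, 3% dropout and daily event times with Breslow ties. There were 4000 trials per scenario.

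| Disagreement at 0.05 | Main-effects Cox (SAP) | Cox stratified on the same factors |
|---|---|---|
| HR 0.70 | 1.6–4.5% (median 2.8%) | 0.8–2.7% (median 1.5%) |
| HR 0.70, log-rank p 0.02–0.10 | 6–19% | 3–11% |
| HR 1.0 | 0.6–1.7% | 0.4–1.0% |

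An independent run with other assumptions (N = 150, 250 or 500; 400 trials per scenario) gave 0.7–5.0% falling to 0.0–2.5%. In that run the rejection rates of the log-rank test and the main-effects Cox model were within about 1 point of each other. The stratified Cox costs a 0.1–1.2% larger standard error.

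**The case against.** **On clinical status.** The endpoint is not alpha-controlled, and the protocol supplies a default. A reader might infer that nothing indicates which model leads. That goes too far: the treatment-only model is the only one in the protocol and opens the SAP paragraph. What stands is that the SAP never confirms it, and that this default is the less powerful choice when baseline status matters. A reader might also infer that two models inflate type I error; the simulated 4.7–6.7% shows no material inflation. Leaving out the strata does not breach SAP 3.3, which promises stratified analysis only for the primary and key secondary endpoints. Adding the strata would create a third model, so leading with the existing baseline-score model is an acceptable alternative.

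**On the hazard ratio.** A reader might infer that the mismatch is an error, or that it threatens the primary conclusion. The documents do not support either. Both forms of Cox model are legitimate, and the one chosen is fixed in text and code. Protocol 8.5.1 prescribes no other, and the log-rank test plainly decides. SAP 6.1.3 already reports a Mantel-Haenszel risk difference and interval on the same eight strata (item 13). Matching the Cox model leaves about half of the disagreement in place (1.5/2.8 = 54% at the medians). This objection stands, so the item is optional.

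**Conclusion.** Minor. The clinical-status part holds: two models, no named lead, no randomisation factors and no entry in SAP 6.4. Its consequence is confined to how a secondary endpoint is read and reported. At an odds ratio of 1.5 the two answers differ at 0.05 in roughly 3–16% of simulated trials, and baseline score is worth between nothing and about 12 power points. These sizes rest on assumed outcome distributions, prognostic effects and stratum shares. They illustrate scale and are not properties of this trial.

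The hazard-ratio part is a reporting preference. Type I error and power are unaffected, and disagreement is a few percent, concentrated near 0.05.

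**What to change.** 1. Before unblinding, name one lead proportional-odds model for Day 15 and Day 29 in SAP 6.2.1 and item 22: treatment, baseline score and the three stratification factors. If a third model is unwanted, lead with the existing baseline-score model, which gives most of the gain.
2. Keep the treatment-only model as supportive, and record the change from Protocol 8.5.2 in SAP 6.4. If the SAP is already final, document it in the clinical study report, as SAP 1 requires.
3. Optional: for the primary endpoint and mortality, report alongside item 23(a) a Cox hazard ratio and interval with the three factors in a STRATA statement, matching item 25. Strata containing one arm contribute nothing, as is already so for the log-rank test and for item 14.

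The cost is a few lines of text and code, with no new data.

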6.1.4. Secondary Analyses of the Primary Efficacy Endpoint

The primary endpoint will also be analyzed for each of the subgroups defined in Section 3.4.

Sensitivity analyses maybe conducted using the following alternative approaches for the primary endpoint.

- A CMH test including stratification factors as strata for the statistical comparison between treatment groups. If a participant prematurely discontinues from the study prior to Day 29 with no event before discontinuation or the IMV/death status is missing, the participant will be considered as with no IMV/death.

- In rare occasions, a participant may be unblinded to site for safety considerations (Gilead remains blinded). Data for such participants after site unblinding may be censored for a sensitivity evaluation.

The sensitivity analyses are for the purposes of evaluating the robustness of the estimates of the primary analysis.

6.2. Secondary Efficacy Endpoints

The key α -controlled secondary endpoint is all-cause mortality through Day 29.

Other secondary endpoints include:

- Initiation of IMV through Day 29
- Time to recovery through Day 29
- Clinical status assessed by the 8-point ordinal scale at Day 15 and Day 29
- RRT-free days (among those without ESKD at baseline) through Day 29
- Proportion of participants with recovery through Day 29

Recovery is defined as achieving category 1, 2, or 3 on the 8-point ordinal scale score, for participants with a baseline score ≥ 4 .

6.2.1. Analysis of Secondary Efficacy Endpoints

The key α -controlled secondary endpoint of all-cause mortality through Day 29 will be analyzed in a similar manner to the primary endpoint.

Initiation of IMV through Day 29 and time to recovery through Day 29 will also be analyzed in a similar manner to the primary endpoint except that a competing risk analysis approach will be used with death as the competing risk.

For analysis on time to recovery through Day 29, two sets of analyses will be conducted:

(1) Time to recovery through Day 29, in which the first recovery without further worsening in the ordinal scale score (ie, a score of > 4) by Day 29 will be considered an event; (2) Time to recovery through Day 29, in which the first recovery (regardless of further worsening or not) will be considered an event.

The clinical status assessed by the 8-point ordinal scale at Day 15 and Day 29 will be analyzed using a proportional odds model including treatment as the independent variable. Two models will be explored; one with baseline score as a continuous covariate and one without baseline score as a covariate. The odds ratio and 95% CI will be provided. The percentage of participants in each category will be summarized by treatment group. The assumption of odds proportionality will be assessed using a score test and reported. Clinical status by study day and change from baseline up to Day 29 will also be summarized by treatment group.

For participants without ESKD at baseline, the number of RRT-free days will be calculated between date of first dose and Day 29. The number of RRT-free days will be calculated as the number of full days from Day 1 to Day 29 that the participant was alive and did not receive RRT. The number of RRT-free days will be summarized by treatment group, and compared between treatment groups using Wilcoxon rank sum test.

The proportion of participants with recovery through Day 29 will be summarized by treatment group, and compared between treatment groups using the CMH test stratified by randomization strata. Similar for time to recovery analysis, two sets of analyses will be conducted: (1) The proportion of participants with recovery through Day 29, in which recoveries without further worsening by Day 29 is considered; (2) The proportion of participants with recovery through Day 29, in which recoveries regardless of worsening status by Day 29 is considered.

The key α -controlled secondary endpoint of all-cause mortality through Day 29 will also be analyzed for each of the subgroups defined in Section 3.4. Other secondary endpoints may also be analyzed for each of the stratification factor subgroups.

For time to event analysis of secondary endpoints, participants with missing outcomes due to premature discontinuation of the study on or prior to Day 29 will be censored at the date of last known status for that endpoint.

Clinical status assessed by the 8-point ordinal scale will be derived by combining the available death, hospital discharge alive and ordinal scale assessment reported by the site, where death supersedes discharge alive and discharge alive supersedes the ordinal scale score reported by the site.

Sites were instructed to report the worst ordinal scale category for each day. Therefore, the ordinal scale result on the day the participant was discharged alive does not necessarily reflect Not hospitalized. The definition of clinical status based on the 8-point ordinal scale is defined as follows:

- If a participant dies on or prior to Day 29, clinical status on the day of death and all subsequent days through Day 29 will be set as 8 (death)
- If a participant is discharged alive on or prior to Day 29, clinical status on the day of discharge alive will be set to 2 (not hospitalized, limitation on activities and/or requiring home oxygen), which is the worst score for a non-hospitalized participant
- If a participant is discharged alive and subsequently re-admitted on or prior to Day 29, and the 8-point ordinal score is not reported on the day of re-admission, the clinical status on the day of the re-admission will be imputed to 7 (hospitalized, on IMV or ECMO), which is the worst score for a hospitalized participant
- For other missing ordinal scores from Day 2 through Day 29, the clinical status will be imputed using the previous day's score (either reported score or imputed score as applicable)

The FAS will be the primary analysis set for the secondary efficacy endpoints.

CCI

[REDACTED]

- [REDACTED]
- [REDACTED]
- [REDACTED]
- [REDACTED]
- [REDACTED]
- [REDACTED]
- [REDACTED]
- [REDACTED]
- [REDACTED]
- [REDACTED]
- [REDACTED]

CCI

CCI

CCI

CCI

CCI

CCI [Redacted]

CCI [Redacted]

[Redacted]

[Redacted]

[Redacted]

[Redacted]

[Redacted]

[Redacted]

[Redacted]

[Redacted]

[Redacted]

[Redacted]

[Redacted]

CCI

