6.9. Ordinal Scale

The ordinal scale is an assessment of the clinical status of a given study day. Each day, the worst (ie, highest ordinal) score from the previous day will be recorded (ie, on Day 3, the highest ordinal score from Day 2 is obtained and recorded for Day 2). The ordinal scale needs to be completed twice on Day 1: prior to randomization (for baseline predose score) and the worst score on Day 1.

The scale is as follows:

- 8) Death
- 7) Hospitalized, on IMV or ECMO
- 6) Hospitalized, on noninvasive ventilation or high-flow oxygen devices
- 5) Hospitalized, supplemental oxygen
- 4) Hospitalized, not requiring supplemental oxygen – requiring ongoing medical care for COVID-19–specific medical care (other than per-protocol RDV administration)
- 3) Hospitalized, not requiring supplemental oxygen – no longer requires ongoing medical care (other than per-protocol RDV/saline as placebo administration)
- 2) Not hospitalized, limitation on activities and/or requiring home oxygen
- 1) Not hospitalized, no limitations on activities

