8.1.3. Secondary End Points

The key (α -controlled) secondary end point of this study is as follows:

- All-cause mortality through Day 29

Other secondary end points include:

- IMV through Day 29
- Time to recovery (defined as satisfying category 1, 2, or 3 by the 8-point ordinal scale)
- Clinical status assessed by an 8-point ordinal scale on Day 15 and Day 29
- RRT-free days (among those without ESKD at randomization) through Day 29
- Recovery through Day 29
- SAEs and AEs leading to investigational drug discontinuation

CCI [REDACTED]

█ [REDACTED]

█ [REDACTED]

█ [REDACTED]

█ [REDACTED]

CCI

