3.5. Multiple Comparisons

To control the overall Type I error in the evaluation of the primary efficacy endpoint and the key secondary efficacy endpoint, the hypothesis testing will be performed in sequential order.

The primary efficacy endpoint will be tested first at the significance level of 0.05. If the primary efficacy endpoint null hypothesis is rejected, the key secondary efficacy endpoint will be tested at the 0.05 significance level; otherwise, the key secondary efficacy endpoint will not be tested.

All other endpoints may be tested using 2-sided tests at the 0.05 significance level without multiplicity adjustment as they are considered secondary **CCI** endpoints.

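### The sustained-recovery analysis in SAP 6.2.1 does not treat a return to category 4 as worsening, although category 4 is not recovered

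*SAP*

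**What the plan says.** SAP 6.2 sets the state to be reached: "Recovery is defined as achieving category 1, 2, or 3 on the 8-point ordinal scale score, for participants with a baseline score ≥ 4". Protocol 8.1.3 uses the same three categories and has no rule about what happens after recovery. Protocol 6.9 describes category 4 as "Hospitalized, not requiring supplemental oxygen – requiring ongoing medical care for COVID-19–specific medical care".

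SAP 6.2.1 then plans two versions of time to recovery. Set (1) takes as the event "the first recovery without further worsening in the ordinal scale score (ie, a score of > 4) by Day 29". Set (2) takes the first recovery whatever follows. For the proportion with recovery, the SAP says "Similar for time to recovery analysis, two sets of analyses will be conducted", but set (1) there refers only to recovery without later worsening and gives no cut-off.

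The scoring rules that matter here are also in SAP 6.2.1. When a participant leaves hospital alive, "clinical status on the day of discharge alive will be set to 2". A re-admission day with no reported score is imputed as 7. Other missing scores carry the previous day's value forward.

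**The concern.** Set (2) already captures first recovery, so set (1) adds information only to the extent that it requires recovery to hold. Its worsening cut-off leaves a gap: a later score of exactly 4 is neither recovered (SAP 6.2) nor worsened (SAP 6.2.1), and the earlier recovery stands. For those participants the two sets give the same event on the same day.

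Two errors follow. Some participants who end Day 29 unrecovered count as having recovered without worsening, and others who recover lastingly are dated too early. The result would also sit awkwardly beside the planned Day 29 clinical status and change-from-baseline summaries. A participant could appear there in category 4 with zero change, and in set (1) as recovered.

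**Working it through.** **Inputs from the documents**
- Recovered: score 1-3, for participants with baseline ≥ 4 (SAP 6.2).
- Worsening in set (1): score > 4, that is 5-8 (SAP 6.2.1).
- Discharge day scored 2, and an unscored re-admission day scored 7 (SAP 6.2.1).
- A baseline score of 4 is possible: inclusion criterion 4 (Protocol 4.2) admits participants on radiographic infiltrates without an oxygen need.
- A reported 4 after re-admission is an expected record: Protocol 6.4 asks for daily ordinal scores through Day 29.

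The documents give no recovery rate or power for this endpoint, so there is no figure of the plan's own to reproduce.

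**Rule applied.** Set (1) event day = first day with score ≤ 3 that has no later score, through Day 29, meeting the worsening cut-off. Set (2) event day = first day with score ≤ 3.

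| Path | Set (1), > 4 | Set (1), ≥ 4 | Set (2) | Day 29 score |
|---|---|---|---|---|
| A: 4 to Day 5; 3 on Days 6-7; 4 on Days 8-29 | Day 6 | no event | Day 6 | 4 |
| B: 4 to Day 5; 3 on Days 6-7; 4 on Days 8-19; discharged Day 20 | Day 6 | Day 20 | Day 6 | 2 |
| C: 5 to Day 5; discharged Day 6; re-admitted, reported 4 on Days 12-29 | Day 6 | no event | Day 6 | 4 |
| D: 5 to Day 5; discharged Day 6; re-admitted, reported 4 on Days 12-20; discharged Day 21 | Day 6 | Day 21 | Day 6 | 2 |
| E: as D, but Day 12 score missing and imputed 7 | Day 21 | Day 21 | Day 6 | 2 |
| F: as D, but score 5 on Days 12-20 | Day 21 | Day 21 | Day 6 | 2 |
| G: discharged Day 6, no return | Day 6 | Day 6 | Day 6 | 2 |

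- In paths A to D the written rule reproduces set (2) exactly.
- Path B is dated 20 − 6 = 14 days early, and path D 21 − 6 = 15 days early.
- Paths D and E differ only in whether the re-admission-day score was entered. The entered 4 keeps the Day 6 recovery, and the missing score moves it to Day 21.
- Paths F and G do not change under ≥ 4.

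**Possible size (all rates assumed).** Let R be the proportion who ever recover, q the share of these who return to exactly 4 and no worse, and r the share of that group who regain 1-3 by Day 29.

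Overstatement of the set (1) proportion = R × q × (1 − r), with R = 0.65 and q = 0.03 to 0.10:
- r = 0: 0.65 × 0.03 = 1.95 to 0.65 × 0.10 = 6.5 percentage points (upper bound)
- r = 0.5: 0.98 to 3.25 points
- r = 0.8: 0.39 to 1.3 points
- r = 1: 0; only the recovery dates are wrong

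**The case against.** The strongest reply is that > 4 is deliberate. The rule is explicit and programmable. SAP 6.2 says when recovery is reached, not what cancels it, and the threshold for losing a state may differ from the one for gaining it. Categories 3 and 4 are both in hospital without oxygen, and oxygen support begins at 5. The purpose of set (1) is inferred, since the SAP does not state it. Set (2) matches the protocol endpoint and is untouched, and participants in category 4 on Day 29 remain visible in the clinical-status tables. A ≥ 4 rule is also sensitive to brief changes: sites record the worst category of each day, so 3 on Days 6-28 followed by a single 4 on Day 29 would give no recovery, and a 4 can be carried forward over missing days.

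Part of this stands. The text cannot show whether > 4 is a slip or a choice, the reach is narrow, and the one-day sensitivity is real. But no visible passage gives a reason for the tolerance. As written it has no time limit (22 days at category 4 in path A), and it extends to re-admission for COVID-19 care after discharge, which is not fluctuation between 3 and 4. It also treats a reported 4 and a missing score on re-admission in opposite ways. Sensitivity to one late score already exists under > 4, where a single 5 on Day 29 cancels the recovery.

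**Conclusion.** The concern holds. Set (1) does not do what its wording suggests for participants who return to category 4: some unrecovered participants are counted as events and some recoveries are dated too early. The number affected cannot be derived from the documents. Under the assumed rates the proportion is overstated by 0 to 6.5 percentage points, and the top of that range requires both the highest assumed relapse share and nobody regaining category 1-3.

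The consequences are limited. Recovery is outside alpha control; SAP 3.5 says "All other endpoints may be tested using 2-sided tests at the 0.05 significance level without multiplicity adjustment". The primary endpoint, the key secondary endpoint and set (2) do not change. The rule applies equally to both arms, and no bias between them is shown. It is still worth correcting, because it affects the interpretation of a named secondary endpoint.

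**What to change.** In set (1) of the time-to-recovery analysis (SAP 6.2.1), change the worsening cut-off from > 4 to ≥ 4, so that any return to a non-recovered category counts. State the same cut-off explicitly in set (1) of the proportion-with-recovery analysis, where it is now available only by cross-reference. Leave set (2) unchanged as the version that matches the protocol.

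The cost is a one-character edit and one added cut-off, using scores already collected. SAP section 1 provides for finalization before unblinding, and the change should be made by then. Set (1) recovery will be somewhat lower or later in both arms, and a single late score of 4 will count against recovery, as a single late 5 already does.
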